PROTOCOL

Background

1. Provide the scientific background, rationale and relevance of this project.

Recent advances in continuous glucose monitors (CGMs) and availability of commercial CGM products to patients with type 1 and type 2 diabetes has made the use of CGM more widespread (1). CGMs work by placing a probe underneath the skin of a patient, into the interstitial space. The probe is an electroenzymatic sensor which uses glucose oxidase to break down glucose to create hydrogen peroxidase and other elements. Hydrogen peroxidase then interacts with a base metal layer of the sensor and is oxidized, which results in release of electrons which creates a current. The current is proportional to the glucose concentration. The current is measured by the probe and transmits a calculated glucose concentration to a receiving device (2). Substances that are widely distributed in body water, and thereby present in the interstitial space, potentially affect this technology. Acetaminophen and aspirin are substances that have been known to affect the accuracy of these devices (3); however, more recently developed CGMs such as the Dexcom G6, were able to demonstrate no interference by acetaminophen (4). Patients with end stage renal disease (ESRD) who are on intermittent hemodialysis (iHD) or peritoneal dialysis (PD) undergo fluid shifts between the interstitial fluid and intravascular space during dialysis treatments. They are also often uremic and have metabolic acidosis (5). These fluid shifts, uremia, acidosis, and volume overload (increase in interstitial fluid volume due to ESRD) have the potential to impact the performance of the most advanced and commercially available CGMs; however, use of CGM in these patients has not yet been studied (3). Moderate to severe CKD is associated with both increase in insulin resistance and decrease in insulin clearance, which results in often unpredictable and labile glucose concentrations and increased risk of hypoglycemia in these patients (6). Use of CGM, and potentially hybrid closed loop insulin delivery systems that are dependent on accurate continuous glucose monitoring, has the potential to improve glucose control and quality of life in these patients (7). We feel this study will be valuable in collecting preliminary data needed with the goal of validating the use of CGM in this patient population.

Objectives/Hypothesis

Our specific aim is to conduct a pilot study to evaluate the accuracy of continuous glucose monitors (CGM) in End Stage Renal Disease (ESRD) patients on intermittent hemodialysis (iHD). Accuracy will be assessed by calculating the mean absolute relative difference (MARD) between CGM values and concurrent finger stick or venous blood glucose (CBG) in these patients during hemodialysis, and on non-dialysis days.

Primary Hypotheses: The MARD between CGM sensor glucose and CBG will be larger on non-HD days than during dialysis.

Study Design: Biomedical

1. Will controls be used?

Yes – patients are their own controls.

▶ **IF YES, explain the kind of controls to be used.**

Accuracy of CGM during HD session will be compared to the accuracy of the CGM on the same patient when they are not in HD session.

2. What is the study design?

Prospective cohort study using blinded 10-day CGM in 30 ESRD patients on iHD who have a diagnosis of type 1 diabetes mellitus or type 2 diabetes mellitus. Will attempt to recruit approximately 15 participants who use insulin therapy though this is not exclusionary. Patients will be requested to perform finger stick blood glucose (FSBG) values using a study glucometer 7 times daily at home (before meals, 2 hours after meals, and at bedtime) for 10 days. A study team member will obtain approximately 12 blood samples from the existing HD IV line during each (three) HD session the CGM sensor is worn. These blood samples will be immediately processed using the *i-STAT System*. While the goal is to have the subject participate in three hemodialysis sessions, two sessions will be acceptable and not considered a study deviation.

3. Does the study involve a placebo?

No

▶ **IF YES, provide a justification for the use of a placebo**

Human Participants

Ages: 18+

Sex: Any

Race: Any

Subjects- see below

1. Provide target # of subjects (at all sites) needed to complete protocol.

30 subjects

2. Describe expected rate of screen failure/ dropouts/withdrawals from all sites.

40%

3. How many subjects will be enrolled at all sites?

Up to 50 subjects

4. How many subjects will sign a consent form under this UVa protocol?

Up to 50 subjects.

Inclusion/Exclusion Criteria

1. List the criteria for inclusion

- Ages 18+
- Type 1 diabetes mellitus on intermittent HD thrice weekly OR Type 2 diabetes mellitus on intermittent HD thrice weekly
- Willingness and ability to comply with scheduled visits and study procedures

2. List the criteria for exclusion

- Noncompliant with HD therapies
- Pregnant women
- Subjects with Hct < 30. This will be determined via the monthly blood draw that the subjects coordinate with entry into the study.

3. List any restrictions on use of other drugs or treatments.

- Hydroxyurea - has been known to interfere with current continuous glucose monitor sensors.

Statistical Considerations

1. Is stratification/randomization involved?

No

► IF YES, describe the stratification/ randomization scheme.

► IF YES, who will generate the randomization scheme?

_____ Sponsor

_____ UVa Statistician. Answer/Response:

_____ UVa Investigational Drug Service (IDS)

_____ Other: Answer/Response:

2. What are the statistical considerations for the protocol?

This is a prospective cohort study of 30 patients with diagnosis of Type 1 or Type 2 diabetes mellitus. The patients enrolled in the study will have a blinded CGM placed for 10 days which will measure interstitial glucose using above referenced electroenzymatic technology and record interstitial blood glucose every 5 minutes. The CGM sensor will be collected 10 days after placement of the sensor. The patients will also check venous blood glucose using a provided glucometer seven times daily on non-HD days. During HD sessions, a study team member will measure blood glucose with the use of an *i-STAT System* point of care machine approximately 10-12 times at the following intervals: q15 minutes x 90 minutes, q30 minutes x 60 minutes, then q60 minutes until HD finished. The results from the *i-STAT System* glucose measurements will be recorded in the study flowsheet. The study glucometers will record and store the results of finger stick blood glucose values which will be collected each day (10 days) after placement of the

sensor. The CGM sensors may be discarded by the study subject. CGM transmitters will be returned to the study team. .

The CGM and study glucometer data will be compared in the 30 patients to assess accuracy in between hemodialysis sessions (HD day + 1 [considered euvoletic] and HD day + 2 day [considered volume overloaded]). MARD will be calculated.

3. Provide a justification for the sample size used in this protocol.

This is a small pilot study to assess MARD (accuracy) of CGM in hemodialysis dependent patients with diabetes.

4. What is your plan for primary variable analysis?

Data scientists at the center for diabetes technology will use CGM, glucometer, and iStat data to calculate the MARD between sensor glucose and venous blood glucose for patients during hemodialysis, and between hemodialysis in different volume states.

5. What is your plan for secondary variable analysis?

Secondary outcomes include duration of HD, volume removed during HD therapy, Basic Metabolic Panel (BMP) prior to HD session including Co2, BUN, glucose, complete blood counts, medications, and daily weight.

6. Have you been working with a statistician in designing this protocol?

No

IF YES, what is their name?

7. Will data from multiple sites be combined during analysis?

No. , Only UVA patients will participate in this study.

7(a). Does the study involve randomization?

IF YES, will randomization be done at each site or among sites?

7(b). Has the sample size calculation considered the variation among sites?

7(c). When combining the data from multiple sites to assess the study results, is the effect of the treatment to be tested (or the association to be tested) assumed to be the same across sites or vary among sites? What is the modelling strategy?

7(d). Is there a common protocol used in all sites?

Study Procedures-Biomedical Research

1. What will be done in this protocol?

Screening (Visit 1):

Potential subjects will be approached during their regularly scheduled dialysis sessions at a UVA dialysis facility. Subjects may be contacted via telephone as well. The subject's provider or study

physician may introduce the study to the potential subject. If interested, a member of the study team will discuss the study in detail and obtain informed consent. Pre-screening inclusion/exclusion questions regarding their possible eligibility for the trial may be reviewed.

Upon consent, the study team member will review the subject's inclusion/exclusion criteria will be assessed by the study team to ensure criteria has been met. The study team member will review the subject's medical history and medications. A serum pregnancy test will be performed for women who are of child-bearing potential. If a subject is pregnant, they will be withdrawn from the study and be advised to seek further confirmation from their primary provider. If the subject meets all criteria, they may continue with the CGM training visit on the same day or at a later date. Fingertick and *i-STAT System* blood glucose values are for study purposes only. Treatment recommendations will not be provided.

The most recent Hemoglobin A1c value that is collected for standard of care and is either dated prior to the study start date or within the data collection period if the duration between the collection date and study start date is greater than 3 months.

Day 1 (Visit 2):

Day 1 may occur on the same day as Screening. At the end of the subject's dialysis session, the study team will insert a DexCom G6 CGM sensor into the participant's abdomen and educate the subject on the use of the DexCom G6 CGM. The CGM will be blinded to both the study physician and participant during the course of study participation – there will be no visible readings during the subject's participation in the study. Selected study team members may incidentally see sensor values when downloading the CGM data. CGM supplies and CGM user's guide will be provided to the participant. Patients will be given a study glucometer, testing supplies, and a scale to measure body weight each day. They will be taught how to use the study glucometer and informed of the schedule for fingerstick monitoring that will occur during the 10 days of wearing the CGM. Subjects will also be asked to weigh themselves every morning with the study-supplied scale and record it in a study record.

Non-Dialysis Days (Days 2, 3, 7, 9, 10):

On days that the subject does not have dialysis, they will perform 7 fingerstick blood glucose tests using the study glucometer. These will be done before meals, after meals, and at bedtime. Subjects will be encouraged to use the study glucometer for any additional blood glucose values they wish to perform.

Subjects will weigh themselves every morning upon voiding and record the results in a study record.

Dialysis Days (Days 4, 6, 8, 11):

On days that the subject has dialysis, they will attend their regularly scheduled dialysis session and perform that run with no change from standard care. During the session, 10-12 samples (1.5

cc) of blood will be drawn from the HD line that is placed for usual care purposes. These samples will occur at approximately the following times:

0m, 15m, 30m, 45m, 60m, 75m, 90m, 120m, 150m, 210m, then every 60 minutes until the end of the dialysis session.

The blood samples will be used to perform a blood glucose test using an *i-Stat System*. The study team will record results and data obtained clinically for the subjects during this time including lab results (e.g. weekly basic metabolic panel, etc...), dialysis run information (including dextrose concentration of the dialysate), vital signs including height and weight, and other clinically relevant medical information. Estimated blood loss will be 20cc per HD session and 60cc per study period. Glucose values collected during the dialysis session will not be used for treatment purposes.

At Home:

Participants will perform 7 fingerstick blood glucose tests using the study glucometer. These will be done before meals, after meals, and at bedtime. Subjects will be encouraged to use the study glucometer for any additional blood glucose values they wish to perform.

Subjects will weigh themselves every morning upon voiding and record the results in a study record.

While the goal is to have the subject participate in three hemodialysis sessions, two sessions will be acceptable and not considered a study deviation.

Final Study Visit (Day 11)

At the final study visit, subjects will remove the CGM sensor from their abdomen. The sensor will be discarded. The CGM transmitter will be returned to the study team. They will discontinue all use of other study equipment (e.g. study glucometer, scale, etc...) and return all study supplies to the study team. Subjects will continue with their standard care for their end-stage renal disease and diabetes management.

The CGM equipment stores the blood glucose values on the transmitter. The study glucometer will be downloaded by study staff once the subject returns the equipment to the team.

Weigh diaries will be completed.

HSR190012: Evaluation of accuracy of continuous glucose monitoring (CGM) in patients with end stage renal disease (ESRD) on intermittent hemodialysis (iHD).

Fingerstick Schedule for Monday, Wednesday, Friday dialysis patients

Sensor placement will occur at the conclusion of the patient's Friday dialysis appointment with the following fingerstick schedule:

Friday (Day 1)	Saturday (Day 2)	Sunday (Day 3)	Monday (Day 4)	Tuesday (Day 5)	Wednesday (Day 6)	Thursday (Day 7)	Friday (Day 8)	Saturday (Day 9)	Sunday (Day 10)	Monday (Day 11)
Dialysis day. Place CGM sensor. Check FSBG before meals and at bedtime.	7 FSBG readings: before & after meals & at bedtime.	7 FSBG readings: before & after meals & at bedtime.	Dialysis day. Obtain 10-12 iStat glucose values during HD session: q15m x 90min, q30m x 60min, q60m until end of HD session; 7 FSBG readings: before & after meals & at bedtime	7 FSBG readings: before & after meals & at bedtime.	Dialysis day. Obtain 10-12 iStat glucose values during HD session: q15m x 90min, q30m x 60min, q60m until end of HD session; 7 FSBG readings: before & after meals & at bedtime	7 FSBG readings: before & after meals & at bedtime.	Dialysis day. Obtain 10-12 iStat glucose values during HD session: q15m x 90min, q30m x 60min, q60m until end of HD session; 7 FSBG readings: before & after meals & at bedtime	7 FSBG readings: before & after meals & at bedtime.	7 FSBG readings: before & after meals & at bedtime.	Dialysis day. Final study visit to return study supplies. No FSBGs.

HSR190012: Evaluation of accuracy of continuous glucose monitoring (CGM) in patients with end stage renal disease (ESRD) on intermittent hemodialysis (iHD).

Fingerstick Schedule for Tuesday, Thursday, Saturday dialysis patients

Sensor placement will occur at the conclusion of the patient's Saturday dialysis appointment with the following fingerstick schedule:

Saturday (Day 1)	Sunday (Day 2)	Monday (Day 3)	Tuesday (Day 4)	Wednesday (Day 5)	Thursday (Day 6)	Friday (Day 7)	Saturday (Day 8)	Sunday (Day 9)	Monday (Day 10)	Tuesday (Day 11)
Dialysis day. Place CGM sensor. Check FSBG before meals and at bedtime.	7 FSBG readings: before & after meals & at bedtime.	7 FSBG readings: before & after meals & at bedtime.	Dialysis day. Obtain 10-12 iStat glucose values during HD session: q15m x 90min, q30m x 60min, q60m until end of HD session; 7 FSBG readings: before & after meals & at bedtime	7 FSBG readings: before & after meals & at bedtime.	Dialysis day. Obtain 10-12 iStat glucose values during HD session: q15m x 90min, q30m x 60min, q60m until end of HD session; 7 FSBG readings: before & after meals & at bedtime	7 FSBG readings: before & after meals & at bedtime.	Dialysis day. Obtain 10-12 iStat glucose values during HD session: q15m x 90min, q30m x 60min, q60m until end of HD session; 7 FSBG readings: before & after meals & at bedtime	7 FSBG readings: before & after meals & at bedtime.	7 FSBG readings: before & after meals & at bedtime.	Dialysis day. Final study visit to return study supplies. No FSBGs.

2. If this protocol involves study treatment, explain how a subject will be transitioned from study treatment when they have completed their participation in the study.

This is not a treatment study. Subjects will discontinue use of study equipment and return all supplies to the study team. Subjects will continue with their usual care and management of their diabetes and end-stage renal disease.

Subject Compliance with Study Procedures

1. Explain how the study team will monitor the subject for compliance with the study procedures.

Research coordinator will check in with patient at each HD session (3 sessions) during study period to review protocol and assess compliance.

2. Describe criteria for when a subject is considered to be non-compliant with study procedures.

If patient obtains <3 finger sticks per day, or misses one HD session, the patient will be considered non-compliant.

Bibliography

2. Berg, E.G. (2014, May). Anatomy of a CGM Sensor. Retrieved February, 2019, from <http://www.diabetesforecast.org/2014/05-may/anatomy-of-a-cgm-sensor.html>
3. Tkattula. (2018, April 11). Safety Information. Retrieved February, 2019, from <https://www.dexcom.com/safety-information#dexcom-g6-brief>

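### The home versus in-session comparison of raw MARD has no check on whether a difference reflects glucose level or rate of change instead of sensor accuracy

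*Combined protocol and SAP*

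**What the plan says.** **Hypothesis and contrast.** Objectives/Hypothesis states: "The MARD between CGM sensor glucose and CBG will be larger on non-HD days than during dialysis". Study Design, item 1 makes the comparison within patient: "Accuracy of CGM during HD session will be compared to the accuracy of the CGM on the same patient when they are not in HD". No size of difference, test or model is given.

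**Analysis.** Statistical Considerations, item 4 says the data scientists will "calculate the MARD between sensor glucose and venous blood glucose for patients during hemodialysis, and between hemodialysis in different volume states". Item 2 adds only that MARD will be calculated. Item 5 (secondary analysis) is a list of variables. Nothing adjusts, matches or stratifies by glucose level or rate of change, and no error measure in mg/dL is planned.

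**Reference samples at home.** Participants use the study glucometer "7 times daily at home (before meals, 2 hours after meals, and at bedtime) for 10 days" (Study Design, item 2).

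**Reference samples in session.** Blood from the dialysis line is run on the i-STAT at "0m, 15m, 30m, 45m, 60m, 75m, 90m, 120m, 150m, 210m, then every 60 minutes until the end of the dialysis session" (Study Procedures, Dialysis Days). That section also has the team record the dialysate dextrose concentration, but gives it no role in the analysis.

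**The concern.** MARD is a relative measure. A fixed error in mg/dL counts for more at a low reference glucose than at a high one. A sensor in interstitial fluid that trails blood glucose also shows a larger error when glucose is moving. Unless sensor error is strictly proportional to glucose and there is no lag, MARD depends on the glucose values sampled as well as on the sensor.

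The two settings are sampled under different conditions by design. With three meals, 3 of the 7 daily fingersticks fall two hours after eating. Session samples follow a fixed clock, densest in the first 90 minutes, in blood that is passing a dialysate containing dextrose. It is reasonable to expect glucose levels and rates to differ between the two, although the documents report no such measurement. Using patients as their own controls does not help, because these conditions change within the same patient.

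At stake is the meaning of the primary result. A difference in the hypothesised direction, or its absence, could come from when and at what level glucose was sampled. The Background presents the study as preliminary data toward validating CGM in this population, so a misattributed direction would carry into the next study.

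**Working it through.** **The plan's own figure.** The only sample-size arithmetic in the documents is enrolment: 30 / (1 − 0.40) = 50, which reproduces. The plan states no MARD, MARD difference, SD, alpha or power, so there is no planned figure to test on this point.

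**Inputs.** From the documents: the sampling schedules, 30 participants, and a CGM value every 5 minutes. Everything else below is assumed: glucose means and SDs, rates, lag and sensor error. The same sensor model is applied in both settings: sensor = G − lag × rate + error, with error SD = √(a² + (bG)²) and G lognormal.

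**Step 1. Level alone, by hand.** For normal error with constant SD a, MARD = 0.798 × a × E(1/G), and for lognormal G, E(1/G) = (1 + CV²)/mean. Take a = 15 mg/dL.
- Session, mean 130, SD 35: CV² = 0.0725. MARD = 0.798 × 15 × 1.0725/130 = 9.9%.
- Home, mean 180, SD 60: CV² = 0.1111. MARD = 0.798 × 15 × 1.1111/180 = 7.4%.

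The gap is 2.5 points against the hypothesis. With mixed error (10 mg/dL plus 7%), simulation gives 8.7% versus 7.5%. With purely proportional error (11%), both are 8.8% and the gap vanishes.

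**Step 2. A wider range of error models, level alone, no lag.** Home minus session, 400,000 simulated pairs per setting:

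| a (mg/dL), b | Home 180, session 140 | Home 140, session 180 |
|---|---|---|
| 0, 0.12 | 0.0 | 0.0 |
| 8, 0.10 | −0.4 | +0.6 |
| 12, 0.08 | −0.9 | +1.3 |
| 15, 0.05 | −1.5 | +2.1 |

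**Step 3. Rate alone, mean 180 in both, 10-minute lag.**
- Rate SD 0.7 mg/dL/min at home and 1.5 in session: about −2.0 to −2.1 points.
- Rate SD 1.2 at home and 0.3 in session: +1.7 to +2.2 points. Of this, 0.0 to 0.5 comes from a wider assumed glucose spread at home (it is present with no lag), which leaves about 1.6 to 1.7 for rate.
- With a 5-minute lag these become about −0.6, and +0.5 to +0.9.

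**Step 4. Level and rate together, 10-minute lag, a = 15, b = 0.05.** Home 180 and slower against session 140 and faster gives −4.4. Home 140 and faster against session 180 and slower gives +4.4. The two effects can also oppose each other: home 180 and faster against session 140 and slower gives +0.2.

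**Step 5. The direction is not fixed.** Take the mixed-error sensor of Step 1 with a 5-10 minute lag and glucose moving 1-2 mg/dL/min on 3 of 7 readings. Home MARD becomes 7.7% to 10.0%. Against a session with no lag error (8.7%), home minus session runs from 7.7 − 8.7 = −1.0 to 10.0 − 8.7 = +1.3. If the same share of session samples carries the same lag error, session MARD is 9.0% to 12.3%, and the gap is 7.7 − 9.0 = −1.3 to 10.0 − 12.3 = −2.3.

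**Step 6. What a shift could do.** The plan names no test. If a paired two-sided 5% test were used with 30 participants, a spurious 2-point shift would reach significance in its own direction with probability Φ(2/(SD/√30) − 1.96). That is 0.95, 0.59 or 0.28 if the SD of the within-patient MARD difference is 3, 5 or 8 points.

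**Step 7. Does a supportive analysis work?** Adjusting for, or banding on, glucose cuts the 2.5-point level artefact of Step 1 to about 0.3. For lag, the form of the slope term matters. With equal glucose, rate SD 1.2 at home and 0.3 in session, and a 10-minute lag, the raw in-session minus home artefact is −2.17. A signed slope leaves it at −2.18, because lag inflates the absolute error whether glucose rises or falls. An absolute slope removes most of it, leaving about +0.5 (a slight over-correction) in that simulation. The residual depends on how noisily the slope is measured. Banding on glucose alone does not address lag.

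**The case against.** The strongest case is that this is a small pilot whose stated aim is descriptive: calculate MARD in each setting. Raw MARD answers that, and no test is specified whose error rate could be distorted. This stands as a limit on severity. It does not remove the point, because the protocol also states a directional hypothesis that rests on comparing the two MARDs.

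Second, no numerical input to the size comes from the documents. This stands in full. A reader might infer that the artefact is about 2 points, or that glucose level and rate are known to differ between settings. The documents support neither: they show different sampling schedules and conditions, and zero lies inside the assumed range.

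Third, a reader might extend the concern to the volume-state comparison, which item 4 mentions in the same sentence. HD day +1 and HD day +2 use the same glucometer and the same seven-reading schedule, so the contrast between meal-tied and clock-timed sampling does not arise there.

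Fourth, glucose adjustment cannot isolate a dialysis effect, because i-STAT is used only in session and the glucometer only at home. This also stands. It is a separate confounder and it limits what any adjusted estimate can show. For the same reason, mere agreement in sign between raw and adjusted estimates would not justify attributing a difference to dialysis.

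**Conclusion.** The concern holds for in-session versus home. The plan contrasts a measure that depends on glucose level and, with sensor lag, on rate of change. It samples the two settings under different conditions and has no analysis that would show whether this explains a difference. Under assumed inputs, an identical sensor could show a spurious MARD difference from 0 (purely proportional error, no lag) to roughly 2-4 points in either direction, so it could create or mask the hypothesised result. The largest values need a 10-minute lag with level and rate acting together. Only the trial's own data can settle the size.

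A reader might conclude that the primary contrast is invalid or certain to be biased. The documents do not support that: raw MARD remains a legitimate description of accuracy in each setting. What is missing is a supportive analysis that limits its interpretation. This is a cheap improvement.

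**What to change.** In Statistical Considerations, item 4, keep raw MARD as the primary measure and prespecify a supportive analysis of the in-session versus home contrast on the same pairs:

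1. MARD in each setting standardised to common glucose bands, with bands defined on the mean of the paired CGM and reference values.
2. Mean absolute difference in mg/dL in each setting.
3. A mixed model for absolute relative difference with a random participant effect, HD state, paired-mean glucose, and the absolute value of the CGM slope over the previous 15 minutes.

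Report the raw and adjusted differences side by side with confidence intervals, without a rule based on agreement in sign. State that i-STAT versus glucometer is fully aligned with setting, so no glucose adjustment can separate a device effect from a dialysis effect.

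The cost is one paragraph and a little more analysis. The 5-minute CGM record and paired references are already collected, so no visits, samples or participants are added. The downside is that adjustment also removes any dialysis effect that acts through glucose level or rate of change. The adjusted estimate therefore supports raw MARD and does not replace it.

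### Do the protocol's day lists call for a fourth session of blood draws on Day 11 and leave Day 5 out?

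*Combined protocol and SAP*

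**What the plan says.** Study Procedures sorts the days after sensor placement under two headings: "Non-Dialysis Days (Days 2, 3, 7, 9, 10" and "Dialysis Days (Days 4, 6, 8, 11".

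Under the first, the instruction is general: "On days that the subject does not have dialysis, they will perform 7 fingerstick blood glucose tests using the study glucometer". Under the second, 10 to 12 samples of 1.5 cc are drawn in each session, at "0m, 15m, 30m, 45m, 60m, 75m, 90m, 120m, 150m, 210m, then every 60 minutes until the end of the dialysis session". An At Home subsection follows. It names no days and says: "Participants will perform 7 fingerstick blood glucose tests using the study glucometer".

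The same part of the protocol gives two totals: "Estimated blood loss will be 20cc per HD session and 60cc per study period", and "While the goal is to have the subject participate in three hemodialysis sessions, two sessions will be acceptable and not considered a study deviation". Study Design also gives three sessions and ties the draws to sessions in which the sensor is worn. Subject Compliance with Study Procedures again counts three sessions.

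The two Fingerstick Schedule tables (Monday/Wednesday/Friday and Tuesday/Thursday/Saturday) agree with each other. Draws are on Days 4, 6 and 8. Seven fingersticks are due on each of Days 2 to 10, including Day 5. Day 11 is a dialysis day used only for the final visit and return of supplies, with no draws listed and fingersticks ruled out.

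**The concern.** Anyone working from the headings alone would find Day 11 among the days on which research blood is drawn and would not find Day 5 at all. The text and the tables then assign different procedures to a named day, and the text directs blood sampling.

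Three things could be at stake. One is a fourth sampled session per subject that the stated blood total does not include. Another is extra CGM/i-STAT pairs in the dialysis arm of the MARD comparison, if the sensor is still in place on Day 11. The last is lost fingersticks on Day 5, a day after dialysis that contributes to the planned comparison of HD day + 1 with HD day + 2 in Statistical Considerations.

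**Working it through.** **Inputs.** Day lists, draw volume and blood loss: Study Procedures. Day-by-day assignments: the two Fingerstick Schedule tables. Session counts: Study Design, Study Procedures, Subject Compliance. Fingerstick duration: Study Design, Statistical Considerations, Day 1 (Visit 2).

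**1. Lists against tables.**

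| | Headings | Tables |
|---|---|---|
| i-STAT draws | 4, 6, 8, 11 | 4, 6, 8 |
| Seven fingersticks (headings with At Home text) | 2, 3, 4, 6, 7, 8, 9, 10, 11 | 2 to 10 |

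The only difference in draws is Day 11. The differences in fingersticks are Day 11 (headings only) and Day 5 (tables only). Day 1 has its own section, so Day 5 is the only day omitted from the lists.

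**2. Blood total.** Formula: sessions x 20 cc.

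- Three sessions: 3 x 20 = 60 cc, which reproduces the stated total.
- Four sessions: 4 x 20 = 80 cc, which does not.

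From the draws alone, 10 to 12 draws x 1.5 cc = 15 to 18 cc per session, or 45 to 54 cc for three sessions and 60 to 72 cc for four. So 60 cc by itself would fit four sessions of ten draws. It is stated together with 20 cc per session, however, and that pair implies three.

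**3. Number of draws.** Three sessions give 30 to 36 per subject and four give 40 to 48. A literal reading of the heading therefore adds at most 12.

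**4. Fingersticks on Day 11.** Study Design, Statistical Considerations and Day 1 (Visit 2) each set the fingerstick period at 10 days. The tables schedule fingersticks on Days 1 to 10, which is 10 days. Day 11 would be an eleventh. The Final Study Visit section ends glucometer use that day, and both tables exclude fingersticks. No conflict remains on this point.

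**5. Day 5.** It lies between the dialysis sessions of Days 4 and 6 on a thrice-weekly schedule, so it is a non-dialysis day and the general rule applies. With that rule, the headings give 10 x 7 = 70 fingersticks over Days 2 to 11, against 9 x 7 = 63 in the tables. The difference of 7 is Day 11, dealt with in step 4.

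**6. What Day 5 would be worth if it were lost.** HD day + 1 falls on Days 2, 5, 7 and 9: 4 x 7 = 28 scheduled readings. Without Day 5 there would be 21, a loss of 7/28 = 25%. That requires staff to ignore both the general rule and the tables, which set out the fingerstick schedule day by day.

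**The case for a change.** The strongest case for a change is about the draws. The Final Study Visit section settles the fingersticks but says nothing about i-STAT sampling. Study Design ties sampling to sessions in which the sensor is worn. The sensor goes in at the end of the Day 1 session and, under Statistical Considerations, comes off 10 days later, which is Day 11. The protocol says "At the final study visit, subjects will remove the CGM sensor from their abdomen", and that visit falls on a dialysis day, but nothing says whether removal comes before or after the session. The worn-sensor wording therefore does not exclude Day 11, the heading names it, and a correction would cost nothing.

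Part of this stands. The heading lacks an exception for Day 11, Day 5 is missing from the list, and the order of sensor removal and dialysis is not stated.

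It does not make a fourth session a serious reading. The worn-sensor phrase itself gives the number as three. Two other sections repeat that number, the blood total requires it, and both tables name the three days. Listing Day 11 as a dialysis day is correct in itself. Once the three sessions are identified as Days 4, 6 and 8, the order of events on Day 11 has no bearing on sampling. Low cost alone is not a reason for a change that alters no result.

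**Conclusion.** The mismatch is real but clerical, and no change to the plan follows. The tables, the three session counts and the 60 cc total all fix the draws on Days 4, 6 and 8. The tables and the general rule give Day 5 its seven fingersticks. Study staff and analysts can reach the intended schedule without a judgement call.

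The worst literal reading adds one sampled session per subject: 80 cc against 60 cc at the protocol's own rate, and up to 12 more draws. Those draws would yield MARD pairs only if the sensor were still worn. No bias in the comparison of dialysis with non-dialysis accuracy is shown, and no Day 5 readings are shown to be lost.

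This conclusion assumes that staff work from the day-by-day tables and the stated counts, and do not treat the two headings as the only instruction.
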